- Disability progression response rate on the Expanded Disability Status Scale Plus (EDSS +) (T25FW, 9-Hole Peg test [9HPT, either hand], EDSS) and for each EDSS + component
- 12- and 24-week confirmed disability improvement response rate on the EDSS + and for each EDSS + component
- Change from Baseline on the Multiple Sclerosis Impact Scale (MSIS-29) total score at Weeks 12, 24, 36, and 52
- Change from Baseline on the Modified Fatigue Impact Scale (MFIS) total score at Weeks 12, 24, 36, and 52
- Change from Baseline on cognition battery at Weeks 12, 24, 36, and 52:
 - Total score of the Symbol Digit Modalities Test (SDMT) Oral Version
 - Total score and T-score of the Brief Assessment of Cognition Verbal Memory - Immediate Recall – BAC App Version
 - Total score and T-score of the Brief Assessment of Cognition Tower of London – BAC App Version
- Change from Baseline on the Low Contrast Visual Acuity (LCVA) assessments at Weeks 12, 24, 36, and 52
- Change from Baseline in select plasma biomarkers for monitoring target binding, neuroprotection and/or neurorestoration at Weeks 12, 24, 36, and 52
- Change from Baseline on the MS Individualized Outcome Assessment (MSIOA) overall symptom score and most bothersome symptom score scale at Weeks 24, and 52
- Change from Week 0 in average daily step count and other activity measures (as described in Section 9.4.3) via home actigraphy with wearable biosensor initiated at Weeks 24, 36, and 52
- Summary of variables from brain MRI at Baseline, Weeks 24 and 52
 - Presence of active lesions T1 Gadolinium (GAD)-enhancing lesions
 - Presence of active new and enlarging T2 hyperintense lesions
 - Cumulative number of total T1 GAD-enhancing lesions
 - Cumulative number of total T2 hyperintense lesions
 - Cumulative number of post-baseline T1 GAD-enhancing lesions

- Cumulative number of post-baseline new and enlarging T2 lesions
- Number of T1 GAD-enhancing lesions at each visit
- Change from Baseline in total volumes of (T1 GAD-enhancing lesions)
- Change from Baseline in total volume of T2 hyperintense lesions
- Change from Baseline in whole brain, gray matter (GM), thalamus, white matter (WM) and normal appearing white matter (NAWM) volumes
- Change from Baseline in regional magnetization transfer ratio (MTR) parameters for whole brain, and NAWM, and MTR for T2 lesions
- Change from baseline in lesion MTR for T1 (GAD)-enhancing lesions and delta MTR

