9.4.11 MRI Parameters

The MRI parameters of interest and analyses are listed in Section 4.3.3.

The number and percentage of subjects with active lesions will be summarized for T1 GAD-enhancing lesions and T2 hyperintense lesions (separately). The difference in the proportion between elezanumab and placebo groups with the 95% confidence interval for the difference based on Wald confidence limits will be presented.

The cumulative number of total T1 GAD-enhancing lesions, cumulative number of total T2 hyperintense lesions, cumulative number of post-baseline T1 GAD-enhancing lesions, cumulative number of post-baseline new and enlarging T2-lesions, will be summarized with continuously and analyzed using an analysis of covariance (ANCOVA). The model for the analysis of the cumulative number of total lesions will include treatment, the stratification factors of diagnosis of MS (PPMS or nrSPMS) and background MS immunotherapy (Yes or No). For the cumulative number of lesions during the treatment period, only subjects with Baseline, Week 24, and Week 52 MRIs will be included. For the cumulative number of lesions post-baseline, only subjects with Week 24 and Week 52 will be included.

The number of T1 GAD-enhancing lesions at each visit (Baseline, Week 24, Week 52) will be summarized categorically with the number and percent of subjects for the following categories: 0, 1, 2, 3, 4, 5, > 5.

The following endpoints will be analyzed using change or percent change from baseline using an ANCOVA model.

- Change from Baseline in total volumes of T1 GAD-enhancing lesions •
- Change from Baseline in total volume of T2 hyperintense lesions
- Percent change from Baseline in whole brain, gray matter (GM), thalamus, white matter (WM) and normal appearing white matter (NAWM) volumes
- Change from Baseline in regional magnetization transfer ratio (MTR) parameters for whole brain, and NAWM, and MTR for T2 lesions
- Change from Baseline in diffusion tensor imaging (DTI) parameters (fractional anisotropy and Apparent Diffusion Coefficient (ADC)) for whole brain, NAWM and T2 hyperintense lesions
- Change from Baseline in cervical spinal cord area, volume and number of lesions
- Change from Baseline in regional MTR for cervical spinal cord lesions
- Change from baseline in DTI parameters (fractional anisotropy and ADC) for cervical spinal cord

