The model for the change from baseline analysis will include treatment, the stratification factors of diagnosis of MS (PPMS or nrSPMS) and background MS immunotherapy (Yes or No), and the baseline value. For each treatment group, the number of subjects, mean, standard deviation, minimum, and maximum, will be presented, as well as the LS means and standard error, and the between group difference, standard error, and 95% confidence interval.

The change from baseline in lesion MTR for T1 GAD-enhancing lesions and delta MTR will be analyzed using an MMRM. The change from baseline will be calculated for each unique lesion within a treatment group. A dummy code will be created based on each

subject-lesion to describe each unique lesion. The model will include the fixed effects of treatment, visit, the stratification factors of diagnosis of MS (PPMS or nrSPMS) and background MS immunotherapy (Yes or No), and the treatment-by-visit interaction, with baseline MTR value as a covariate. The RANDOM statement will be used for each subject. The REPEATED statement will be used for visit with blocks in the covariance matrix identified by unique lesion nested within subject nested within treatment group. The unstructured covariance structure will be used to estimate the within subject variancecovariance. If the model fails to converge, the first order autoregressive (AR[1]) covariance structure will be substituted. If the model still fails to converge, the compound symmetry (CS) covariance structure will be substituted. Denominator degrees of freedom will be computed using the Kenward-Roger method.

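### The SAP does not say how its cumulative total T2 lesion count is formed, and on either reading the count mostly reflects lesions present before treatment

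*SAP*

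**What the plan says.** SAP 4.3.3 introduces the brain imaging list with "Summary of variables from brain MRI at Baseline, Weeks 24 and 52". Two T2 entries in that list are cumulative: "Cumulative number of total T2 hyperintense lesions" and, separately, "Cumulative number of post-baseline new and enlarging T2 lesions". Neither comes with a derivation.

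SAP 9.4.11 handles both in one sentence with the two corresponding T1 GAD-enhancing counts and assigns them to ANCOVA. Two inclusion rules follow. The first is "For the cumulative number of lesions during the treatment period, only subjects with Baseline, Week 24, and Week 52 MRIs will be included". The second is "For the cumulative number of lesions post-baseline, only subjects with Week 24 and Week 52 will be included".

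The model for the totals is given as "The model for the analysis of the cumulative number of total lesions will include treatment, the stratification factors of diagnosis of MS", followed by background immunotherapy. No baseline lesion count is named. By contrast, the change-from-baseline ANCOVA in the same section does include the baseline value. That model is applied, among others, to T2 lesion volume and to the number of cervical cord lesions.

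The section uses lesion-level identity only for the magnetization transfer analysis of T1 GAD-enhancing lesions: "The change from baseline will be calculated for each unique lesion within a treatment group". There is no corresponding rule for T2 counts.

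**The concern.** The two T2 counts differ in kind. New and enlarging lesions are events, which can be added over scans. The total on a scan is a standing stock, and a lesion that persists appears in it each time. The SAP calls both cumulative and does not say whether a lesion seen on several scans is counted once.

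Two programmers could therefore produce values that differ about threefold, and a reader would take either as a number of lesions.

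The second problem does not depend on which derivation is meant. The count is described as covering the treatment period, yet it needs the pre-dose scan, which Protocol Appendix D places at Screening. All pre-treatment lesions enter the outcome, and the stated model does nothing to remove them. An arm comparison meant to describe activity on treatment would then be driven largely by differences in lesion load at entry.

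**Working it through.** The SAP gives no figure for this variable, so there is nothing to reproduce. The check compares the two possible derivations.

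**Inputs**
- Three contributing scans: Baseline, Week 24 and Week 52 (SAP 4.3.3 and 9.4.11).
- B = lesions at baseline, n1 = new by Week 24, n2 = new between Weeks 24 and 52. The documents give none of these. Assumed range: B from 10 to 60, with 0 to 2 new lesions per interval.
- All lesions are taken to persist. If some disappear, the multiples below are upper limits.

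**Formulas**
- Reading 1, scan totals added: B + (B + n1) + (B + n1 + n2) = 3B + 2n1 + n2. The share from baseline lesions is 3B/(3B + 2n1 + n2).
- Reading 2, baseline plus new: B + n1 + n2. The share from baseline lesions is B/(B + n1 + n2).

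| B | n1, n2 | Reading 1 | Reading 2 | Ratio | Baseline share, reading 1 | Baseline share, reading 2 |
|---|---|---|---|---|---|---|
| 10 | 0, 0 | 30 | 10 | 3.00 | 100% | 100% |
| 10 | 1, 1 | 33 | 12 | 2.75 | 30/33 = 91% | 10/12 = 83% |
| 10 | 2, 2 | 36 | 14 | 2.57 | 30/36 = 83% | 10/14 = 71% |
| 30 | 1, 1 | 93 | 32 | 2.91 | 90/93 = 97% | 30/32 = 94% |
| 30 | 2, 2 | 96 | 34 | 2.82 | 90/96 = 94% | 30/34 = 88% |
| 60 | 1, 1 | 183 | 62 | 2.95 | 180/183 = 98% | 60/62 = 97% |
| 60 | 2, 2 | 186 | 64 | 2.91 | 180/186 = 97% | 60/64 = 94% |

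Over this range, reading 1 is 2.57 to 3.00 times reading 2. Baseline lesions supply at least 83% of the value under reading 1 and at least 71% under reading 2. In general they are the larger part whenever 3B > 2n1 + n2 (reading 1) or B > n1 + n2 (reading 2).

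**Which reading the text favours**
- The T1 GAD and T2 totals share one sentence and one scan rule. For T1 GAD-enhancing lesions, SAP 4.3.3 lists a number at each visit and no new-lesion count, so the simplest cumulative total is the sum of the visit counts. The T2 total, treated alike, would be summed too.
- The two inclusion rules differ only in which scans are required, which fits accumulation over scans.
- Reading 2 needs a count of new T2 lesions alone. The SAP names only a combined new and enlarging count, and an enlarging lesion has already been counted.

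These points favour reading 1 but do not establish it.

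**The alternative**
Change in lesion number is (B + n1) − B = n1 at Week 24 and (B + n1 + n2) − B = n1 + n2 at Week 52. B cancels. With B = 30 and one new lesion per interval, the values are 1 and 2.

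**The case against.** A reader might infer that the SAP counts each persisting T2 lesion three times. The documents do not say so. The inclusion sentence settles who is analysed, not how the variable is built, and a baseline-plus-new count needs the same three scans. SAP 4.3.3 lists no per-visit T2 total for the brain, which is the quantity that would be summed. SAP 11.1 also refers to a statistical programming plan, which is not among the documents and may hold the derivation. This objection stands: triple counting is a likely reading, not a documented fact.

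Three further inferences go too far.
- **A treatment difference in new lesions would be overstated by 46%.** With a constant new-lesion rate, reading 1 gives (2 × 24 + 28)/52 = 1.46. That holds only under reading 1, and new activity has its own endpoint, which is unaffected.
- **Precision would be three times worse.** The factor 3 on baseline lesions is largely a change of unit: for that component the estimate, standard error and interval all scale together. The documents also give no standard deviation from which to compute one.
- **The arm comparison would be biased.** Subjects are randomised, so unadjusted baseline burden adds noise and chance imbalance, not a systematic shift.

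It is also fair that T2 burden is assessed through volume change with baseline in the model, and that this is one of many exploratory MRI summaries.

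None of this meets the narrower point. The more favourable reading still puts every pre-treatment lesion into the outcome, without a baseline count in the stated model.

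**Conclusion.** The concern holds in limited form. The SAP leaves the derivation of the cumulative total T2 count open. Summing scan totals is the more natural reading and gives a value about 2.6 to 3 times the number of distinct lesions over the assumed range. Under either derivation the value is mainly pre-treatment burden. That rests on persisting lesions and on baseline counts well above the number of new lesions; the documents supply neither figure.

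The severity is minor. The variable is exploratory, the ORS and EDSS+ endpoints do not use it, and the post-baseline new and enlarging T2 count excludes lesions that merely persist from baseline.

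**What to change.** In SAP 4.3.3 and 9.4.11, replace the cumulative total T2 count with change from baseline in T2 lesion number at Weeks 24 and 52. Analyse it with the change-from-baseline ANCOVA already in 9.4.11: treatment, the two stratification factors and the baseline value. Add one sentence stating that standing T2 counts are not added across scans. Leave the post-baseline new and enlarging T2 count as it is.

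Redefining the variable only as baseline plus new lesions would settle the counting but would still leave baseline burden in the outcome.

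The cost is one derived variable and a short text change, with no new scans. It does require per-scan T2 lesion counts from the MRI reader, which the documents do not confirm are supplied. If the tables already exist, state the derivation used and relabel or rederive the variable.

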3.7 Exploratory Endpoints

- 1. Disability improvement response rate on the T25FW, 9HPT, either hand, and EDSS at Weeks 12, 24, 36, and 52, and the EDSS + at Weeks 12, 24, and 36.
- 2. Change from Baseline on the T25FW and 9HPT, either hand, at Weeks 12, 24, 36, and 52
- 3. Disability progression response rate on the EDSS + (T25FW, 9HPT, either hand, EDSS) and for each EDSS + component
- 4. 12- and 24-week confirmed disability improvement response rate on the EDSS + (T25FW, 9HPT, either hand, EDSS) and for each EDSS + component
- 5. Change from Baseline on the MS Impact Scale (MSIS-29) version 2 at Weeks 12, 24, 36, and 52
- 6. Change from Baseline on the Modified Fatigue Impact Scale (MFIS) at Weeks 12, 24, 36, and 52
- 7. Change from Baseline on cognition battery at Weeks 12, 24, 36, and 52:
 - Symbol Digit Modalities Test (SDMT) Oral Version
 - Brief Assessment of Cognition Verbal Memory Immediate Recall BAC App Version

- Brief Assessment of Cognition Tower of London BAC App Version
- Change from Baseline on the Low Contrast Visual Acuity (LCVA) assessments at Weeks 12, 24, 36, and 52
- 9. Change from Baseline in plasma biomarkers at Weeks 12, 24, 36, and 52
- 10. Change from Baseline on the MS Individualized Outcome Assessment (Multiple Sclerosis Individualized Outcome Assessment [MSIOA]) scale at Weeks 24 and 52
- 11. Change from Baseline in one week average daily step count and other activity measures (via home actigraphy with wearable biosensor) initiated at Weeks 24, 36, and 52

MRI Endpoints

The following imaging tests will be conducted. Details will be provided in the Statistical Analysis Plan (SAP).

- Lesion counts and volumes
- Brain and spinal cord atrophy measures
- Magnetization transfer ratio (MTR)
- Diffusion tensor imaging (DTI)

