7.3 Statistical Analyses for Efficacy

The ORS scores will be summarized descriptively (including n, mean, standard deviation, minimum, median, and maximum) along with the 95% confidence interval at each visit. The frequency and percentage of ORS for –4 to +4 will also be provided by treatment group at each visit. The ORS for each treatment group at scheduled visits and overall will also be estimated using a mixed-effect model for repeated measures (MMRM) including treatment group, visit, treatment-by-visit interaction, and stratification factors as fixed effects, with the baseline values for the ORS components as covariates.

For other continuous efficacy endpoints, the mean, standard deviation, median, minimum and maximum will be reported for each treatment group. The treatment comparison will be conducted using MMRM model including treatment group, visit, treatment-by-visit interaction, and stratification factors as fixed effects and the baseline value associated with the endpoint as a covariate.

For binary efficacy endpoints, the frequency and percentage will be provided by treatment group. The treatment comparison will be conducted using a logistic regression model adjusted for the stratification factors and baseline score associated with the endpoint.

All efficacy endpoints will be analyzed on mITT population. The RF and MMIA Sets will be used for the primary and other efficacy analyses as specified in the SAP.

Sample Size Estimation

Approximately 90 subjects will be equally randomized 1:1:1 to each treatment group (30 subjects in each treatment group, with a target of 20 PPMS subjects and approximately 10 SPMS subjects per treatment group). There is limited prior data to estimate the magnitude of effect and variance for a neurorestorative therapy. The sample size was therefore selected based on operational feasibility, variance seen in prior MS trials, and the likelihood of predicting success in subsequent phases of development.

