4.7 Missing Data Imputation

For continuous efficacy variables, data will be summarized using a mixed-effect model for repeated measures (MMRM) model unless otherwise specified. Missing data will not be imputed before applying an MMRM model.

The MMRM model relies on a missing at random (MAR) assumption.

For sensitivity analyses of the primary and secondary efficacy variables, missing values will be imputed using multiple imputation (MI) and categorized as responder/non-responder after imputation. The MI model also relies on a MAR assumption.

Justification for the MAR Assumption:

The COVID-19 pandemic is interfering with the conduct of many ongoing trials, with potential impact on treatment duration and the collection, analysis and the interpretation of clinical trial data. Some protocol-specified visits in this clinical trial may be impacted due to COVID-19 infection or logistical restrictions during the pandemic. For example, some scheduled visits may be missed due to self-quarantine or local government restrictions on travel; some visits may also be delayed or canceled due to healthcare resource constraints during the pandemic. These missed visits will be recorded in the database. The probability of having missed visits and missing data due to COVID-19 infection or logistical restrictions related to the COVID-19 pandemic can be reasonably assumed to be unrelated to the unobserved values conditional on the observed data. Therefore, for the purpose of statistical analysis, it is reasonable to assume that these missing data are missing at random (MAR) and the statistical models that require MAR assumption are appropriate. In some cases, sensitivity analyses may be performed to assess the impact of missing data and the robustness of the conclusion.

Where noted, summaries as observed will not impute values for missing evaluations, and thus a subject who does not have an evaluation on a scheduled visit will be excluded from the as observed for that visit.

Safety variables will be summarized as observed.

5.0

Analysis Sets and Important Subgroups

5.1 **Analysis Sets**

The Modified Intent-to-Treat (mITT) Population includes all randomized subjects who receive at least 1 dose of study drug. Subjects will be grouped according to treatment as randomized. The mITT analysis set will be used for all demographic and efficacy analyses, unless otherwise noted.

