9.4 Other Efficacy Analyses

Change from baseline treatment comparison at each visit will be conducted using an MMRM model including treatment group, visit, treatment-by-visit interaction, and stratification factors as fixed effects, the baseline values associated with the endpoint as covariates. The REPEATED statement will be used for visit with blocks in the covariance matrix identified by subject nested within treatment group. The unstructured covariance structure will be used to estimate the within subject variance-covariance. If the model fails to converge, the first order autoregressive (AR[1]) covariance structure will be substituted. If the model still fails to converge, the compound symmetry (CS) covariance structure will be substituted. Denominator degrees of freedom will be computed using the Kenward-Roger method.

For binary efficacy endpoints, the frequency and percentage will be provided by treatment group unless otherwise noted.

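### SAP 9.4.11 analyses the listed subject-level MRI change endpoints by ANCOVA with no visit term and no stated visit, an unexplained exception to the general MMRM rule that costs a little precision and needs a stronger missing-data assumption

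*SAP*

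**What the plan says.** **MRI rule.** SAP 9.4.11 introduces its list of change endpoints with "The following endpoints will be analyzed using change or percent change from baseline using an ANCOVA model". The list covers T1 gadolinium-enhancing (GAD) and T2 lesion volumes, brain volumes, MTR (whole brain, normal-appearing white matter, T2 lesions), DTI, and the cervical cord measures. The terms given are treatment, MS type, background immunotherapy and the baseline value. There is no visit effect, no treatment-by-visit interaction and no repeated-measures structure. The section does not say at which visit or visits the model is fitted.

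**Scans.** SAP 4.3.3 heads the brain list "Summary of variables from brain MRI at Baseline, Weeks 24 and 52" and gives Weeks 24 and 52 for the cord. The activity schedule (protocol Appendix D) also marks an MRI at the Early Discontinuation visit.

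**General rule.** For continuous efficacy endpoints other than the ORS, protocol 7.3 says "The treatment comparison will be conducted using MMRM model including treatment group, visit, treatment-by-visit interaction, and stratification factors as fixed effects". SAP 9.4, the parent of 9.4.11, says "Change from baseline treatment comparison at each visit will be conducted using an MMRM model including treatment group, visit, treatment-by-visit interaction, and stratification factors".

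**Room for exceptions.** Under its MRI heading, protocol 3.7 says "The following imaging tests will be conducted. Details will be provided in the Statistical Analysis Plan (SAP". SAP 4.7 reads "For continuous efficacy variables, data will be summarized using a mixed-effect model for repeated measures (MMRM) model unless otherwise specified".

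**Other endpoints.** In 9.4.11 itself, T1 GAD lesion MTR and delta MTR are analysed by MMRM, so they fall outside this point. The MSIOA, also collected only at Weeks 24 and 52, gets MMRM under SAP 9.4.5.

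**The concern.** With two post-baseline scans per subject, an ANCOVA fitted at Week 52 uses only subjects who have a Week 52 scan. A subject whose only post-baseline scan is at Week 24 contributes to a Week 24 contrast, if one is made, but not to Week 52. An MMRM would use that scan through its correlation with Week 52.

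Two things follow. First, some precision is given up in a trial with about 30 subjects per arm. Second, the missing-data assumption changes. SAP 4.7 argues for MAR conditional on the observed data, and the Week 24 scan is part of those data. A by-visit ANCOVA does not condition on it, so it needs missingness to be ignorable given treatment and the baseline covariates alone, which is a stronger assumption than the one the SAP defends. SAP 11.1 reports increased missing data because of COVID-19, so the question is not purely theoretical.

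No reason is given for the exception. Having only two visits cannot be the reason, since the MSIOA has the same two visits and gets MMRM. Nor can the imaging source, since T1 GAD lesion MTR from the same scans gets it too.

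**Working it through.** **Inputs from the documents.** About 30 per arm and overall dropout of about 10% (SAP 4.4); scans at Weeks 24 and 52 (SAP 4.3.3, protocol Appendix D). Neither document gives a power figure, a missing-scan rate or a between-visit correlation for any MRI endpoint. The only power statement is for the primary design, and it reproduces: 30 × 0.9 = 27 per arm, effect size 0.59 and one-sided alpha 0.1 give 80.8% by the noncentral t, against about 80% stated. It says nothing about MRI.

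**Assumptions.** m is the share of subjects with a Week 24 scan but no Week 52 scan, taken as 10%, 20% or 30%; 10% borrows the planned overall dropout. ρ is the correlation of the Week 24 and Week 52 changes given the covariates, taken as 0.6 to 0.9.

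**Precision at Week 52.** For two visits with monotone, random missingness:

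Var(MMRM) / Var(ANCOVA) = 1 − ρ²m

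Excess SE of ANCOVA = 1/√(1 − ρ²m) − 1

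| m | ρ = 0.6: variance ratio | excess SE | ρ = 0.9: variance ratio | excess SE |
|---|---|---|---|---|
| 10% | 1 − 0.36 × 0.1 = 0.964 | 1.8% | 1 − 0.81 × 0.1 = 0.919 | 4.3% |
| 20% | 0.928 | 3.8% | 0.838 | 9.2% |
| 30% | 0.892 | 5.9% | 0.757 | 14.9% |

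In subjects: at m = 10% and ρ = 0.7, ANCOVA has 27.0 per arm at Week 52 and MMRM the equivalent of 27.0 / (1 − 0.49 × 0.1) = 28.4. If ρ = 0 or no Week 52 scan is missing, the loss is zero.

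A simulation (three arms of 30, 3,000 runs per setting, ρ from 0.5 to 0.9, random missingness) gave SE ratios of 1.008 to 1.043 at 10%, 1.025 to 1.101 at 20% and 1.044 to 1.150 at 30%, in line with the formula.

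**Bias at Week 52, one-arm scenario.** Assume that in one arm only, the probability p of a missing Week 52 scan follows a logistic model with slope 1 on the standardised Week 24 change, and that ρ = 0.8. The mean Week 24 change among those still observed then shifts by E[p(1 − p)] / (1 − m) in absolute size, and the Week 52 mean by ρ times that:

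- m = 10%: 0.082 / 0.9 = 0.091; × 0.8 = 0.07 SD
- m = 20%: 0.139 / 0.8 = 0.173; × 0.8 = 0.14 SD
- m = 30%: 0.177 / 0.7 = 0.253; × 0.8 = 0.20 SD

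The MMRM conditions on the Week 24 value, so its bias is about 0.

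**Bias, same rule in every arm.** With the same dependence on Week 24 in all three arms and a true effect of 0.50 in one active arm, the simulation averages were 0.44 to 0.48 for ANCOVA and 0.49 to 0.51 for MMRM. The shortfall is 0.02 to 0.06, smaller than in the one-arm case.

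**The case against.** A reader might infer that the SAP breaks the protocol. It does not. Protocol 3.7 hands MRI details to the SAP, SAP 4.7 lets an analysis depart from MMRM where the SAP specifies one, and SAP 9.1 already sets MRI apart when it describes the exploratory summaries. This objection stands in full.

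A reader might also infer a large loss. The only documented rate is 10% overall dropout, where the SE penalty is a few percent. The relevant share could be lower still, since subjects who leave before Week 24 help neither model. The early-discontinuation MRI might fill some Week 52 values. The SAP text gives no rule for windowing it, and the SAP refers to a separate programming plan that is not available here, so this cannot be settled.

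Nor do the documents show that bias will occur. The one-arm mechanism and its slope are assumed. If scans were missed for the logistical reasons in SAP 4.7 and those are unrelated to the MRI result, the ANCOVA is unbiased too.

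Finally, because the visit is unstated, it would be too broad to say that Week 24 data are ignored. If the model is fitted at each visit, they serve the Week 24 contrast. What remains is that they do not inform Week 52, and that the choice is unexplained. A baseline-adjusted ANCOVA is a valid method; nothing above makes it the better one here.

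**Conclusion.** The point holds as a minor, specific improvement. For the listed endpoints the SAP leaves the visit unstated and uses a model that, if run by visit, takes nothing from Week 24 at Week 52.

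The cost in precision is small at the planned dropout and becomes noticeable only if 20% to 30% of subjects have a Week 24 scan without a usable Week 52 scan and the two changes are highly correlated. The bias figures illustrate what the stronger missing-data assumption could cost; they are not a forecast. Both sets of numbers rest on assumed rates and correlations, and both shrink if early-discontinuation scans are used at Week 52.

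The endpoints are exploratory in a Phase 2a study with no multiplicity adjustment. The primary and secondary analyses, the significance level and the sample size are not affected.

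**What to change.** In SAP 9.4.11, for the listed change and percent-change endpoints only, replace the ANCOVA by the MMRM of SAP 9.4: treatment, visit (Weeks 24 and 52), treatment-by-visit interaction, the two stratification factors and the baseline value, with unstructured covariance and Kenward-Roger degrees of freedom. Report the Week 24 and Week 52 contrasts from that model. T1 GAD lesion MTR and delta MTR stay as they are.

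If the ANCOVA is kept, state the visit or visits at which it is fitted, how early-discontinuation scans are windowed, and why MMRM was not used.

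The cost is about one sentence in the SAP and reuse of MMRM code already needed for other endpoints. No new data are required. Protocol Appendix E reports that a planned efficacy analysis has already taken place; if it included these endpoints, show the MMRM beside the ANCOVA and label it as added afterwards.
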